13.1.7 All-cause mortality rate

All-cause mortality (from Baseline to Day 28) rate will be summarized by treatment group. Associated 95% CI for the proportion will be provided for each treatment group using Clopper-Pearson method.

13.2 Correlation Analysis for Preliminary Efficacy Outcomes

Correlation of biomarker levels to preliminary efficacy outcomes will be assessed between changes from Baseline in preliminary efficacy outcomes with Baseline levels of inflammatory biomarkers using Fisher's transformation of Pearson's or Spearman's correlation as detailed below.

The Fisher's transformation of Pearson correlation coefficient, 95% CI and corresponding P-value will be presented for the correlation between the following Baseline biomarker parameters and change from Baseline to Day 7 and Day 14 in PaO₂/FiO₂ ratio.

- Baseline CRP
- Baseline Ferritin and lymphocyte counts

The above analysis will be repeated based on assessments that took place on Study Day 7 and Study Day 14. For any patients with missing Day 7 results, the Day 7 results will be imputed using the last value reported prior to study day 7. Similarly, Day 14 missing observations will be imputed with the last available assessment that took place after study day 7 and prior to study day 14.

The Fisher's transformation of Spearman rank correlation will also be used to assess the correlation between the same Baseline biomarker profiles, as well as the PaO₂/FiO₂ ratio, and change from Baseline to Days 7, 14, and 28 in WHO ordinal scale.

This analysis will be repeated based on assessments that took place on Study Day 7, Study Day 14 and Study Day 28. For any patients with missing Day 7 results, the Day 7 results will be imputed using the last value reported prior to study day 7. Similarly, Day 14 missing observations will be imputed with the last available assessment that took place after study day

7 and prior to study day 14. Day 28 missing observations will be imputed with the last available assessment that took place after study day 14.

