**Clinical Efficacy Endpoints:**

- Change from Baseline to Day 7 and Day 14 in PaO2/FiO2 ratio
- Time to improvement of oxygenation defined as oxygen saturation (pulse oximetry)  $>93\%$  and increased  $\geq 1\%$  from Baseline breathing only room air in the 48 hours preceding the measurement during the study (Baseline to Day 28)
- Number of days without oxygen use during the study (Baseline to Day 28)
- Change from Baseline to Days 7, 14 and 28 in the score of the WHO ordinal scale
- Proportion (%) of patients with clinical improvement defined as a reduction of 2 points in the WHO ordinal scale during the study (Baseline to Day 28).
- Number of days hospitalized during the study (Baseline to Day 28)
- Proportion (%) of patients free of respiratory failure during the study (Baseline to Day 28)

- All-cause mortality rate during the study (Baseline to Day 28)

Changes in clinical efficacy endpoints in patient populations with different Baseline levels of inflammatory biomarkers to assess the correlation of biomarker profile to clinical efficacy outcomes

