	
 • Time to improvement of oxygenation defined as oxygen saturation (pulse oximetry) $>93\%$ and increased by $\geq 1\%$ from Baseline breathing only room air in the 48 hours preceding the measurement during the study (Baseline to Day 28) • Number of days without oxygen use during the study (Baseline to Day 28) • Change from Baseline to Days 7, 14, and 28 in the score of the World Health Organization (WHO) ordinal scale • Proportion (%) of patients with clinical improvement defined as a reduction of 2 points in the WHO ordinal scale during the study (Baseline to Day 28). • Number of days hospitalized during the study (Baseline to Day 28) • Proportion (%) of patients free of respiratory failure during the study (Baseline to Day 28) • All-cause mortality rate during the study (Baseline to Day 28) 
Changes in clinical efficacy endpoints in patient populations with different Baseline levels of inflammatory biomarkers to assess the correlation of biomarker profile to clinical efficacy outcomes.
 
2) To assess the effects of SIR1-365 on multiple inflammatory biomarker levels including CRP, ferritin, lymphocyte and neutrophil counts, cytokines and chemokines
 
Inflammatory Biomarker Measures:
 
 • Change from Baseline to Day 7 and to Day 14 in plasma CRP levels • Time and number of the patients to reach 50% reduction from Baseline in plasma CRP level during the treatment period (Baseline to Day 14) • Change from Baseline to Day 7 and Day 14 in inflammatory biomarker levels including ferritin, lymphocytes, and neutrophil to lymphocyte ratio • Change from Baseline to Day 7 and Day 14 in serum cytokine levels including IL-6, TNF-α, IL-1β, IL-7, IL-8, IL-9, IL-10, total IL-18, G-CSF, and GM-CSF • Change from Baseline to Day 7 and Day 14 in serum chemokine levels including CXCL-1, CXCL-9, CXCL-10, IP-10, MCP-1 and MIP-1α
--	---

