11.9 Correlation Analysis for Safety Outcomes

Correlation of biomarker levels to safety outcomes will be assessed between the proportions of safety outcomes, i.e TEAE and SAE with Baseline levels of inflammatory biomarkers using logistic regression analysis as detailed below.

A logistic regression model will be fitted to the binomial presence (Yes/No) of adverse events per patient as a function of treatment, Baseline biomarker and the interaction between treatment and Baseline biomarker as fixed effects.

The regression coefficients, 95% CI and corresponding P-values will be reported and used to assess the association between the following Baseline biomarker parameters and the proportion of TEAE and SAE per treatment group:

- Baseline CRP
- Baseline Ferritin and lymphocyte counts

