12.3 Subgroup Analysis

Subgroup analyses will be performed on the CRP levels, PaO₂/FiO₂ ratio and WHO ordinal scale to summarize the treatment effects across countries based on mITT set by repeating the analysis as described for biomarker in [Section 14.1.1 CRP Levels](#) and preliminary efficacy

endpoints in [Section 13.1.1 PaO₂/FiO₂ ratio](#) and [Section 13.1.4 WHO ordinal scale](#) by country (USA, Mexico and Pakistan).

A subgroup analysis will also be performed on the duration of hospitalization after treatment, to summarize the treatment effect on those patients who completed study treatment, by repeating the analysis as described for hospitalization in [Section 13.1.5 Days of Hospitalization](#) for the subgroup of patients that completed treatment. Completed patients are defined as those patients that indicated 'Yes' to 'Was Study Treatment Completed?' on the End of Treatment CRF.

A subgroup analysis will also be done for the derived PaO₂/FiO₂ ratio to summarize the treatment effects across countries based on mITT set, by repeating the analysis as described for biomarker in [Section 13.1.1.1](#) by country (USA, Mexico and Pakistan).

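### SAP 13.2 relates efficacy to baseline biomarkers by correlation alone, with no treatment term, so a pooled coefficient cannot tell a prognostic marker from one that modifies the drug effect

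*SAP*

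**What the plan says.** **Biomarkers and efficacy.** The SAP's outcome table (section 4) lists "Changes in clinical efficacy endpoints in patient populations with different Baseline levels of inflammatory biomarkers", and the protocol's wording of the aim is "to assess the correlation of biomarker profile to clinical efficacy outcomes". Protocol 8.1 and 10.3.1 leave the details to the SAP. SAP 13.2 has the correlation "assessed between changes from Baseline in preliminary efficacy outcomes with Baseline levels of inflammatory biomarkers" and then specifies: "The Fisher's transformation of Pearson correlation coefficient, 95% CI and corresponding P-value will be presented for the correlation" between baseline CRP, ferritin and lymphocytes and the change in PaO2/FiO2 at Days 7 and 14. A Spearman version covers the change in WHO score at Days 7, 14 and 28 and adds baseline PaO2/FiO2 as a predictor. No treatment term appears, and 13.2 does not say whether the coefficients are pooled or by arm. The table titles for these analyses in SAP Appendix 5 do not settle it either.

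**Biomarkers and safety.** SAP 11.9 models the occurrence of TEAEs and SAEs "as a function of treatment, Baseline biomarker and the interaction between treatment and Baseline biomarker as fixed effects".

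**Country.** SAP 12.3 covers CRP, PaO2/FiO2 and the WHO scale "to summarize the treatment effects across countries based on mITT set by repeating the analysis as described for biomarker in" the CRP section, and likewise for the two efficacy endpoints, "by country (USA, Mexico and Pakistan"). No comparison between the countries is specified.

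**Elsewhere.** The exploratory ANCOVA in SAP 13.3 has main effects only, so it does not fill either gap.

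**The concern.** The same SAP includes an interaction when it asks how a baseline biomarker relates to safety, and leaves it out, without a reason, when it asks the same about efficacy. The efficacy question sits under the objective of assessing the drug's clinical efficacy. A correlation with no treatment term says only whether patients with high CRP, for example, improve more or less on the whole. It says nothing about whether SIR1-365 does more or less for them.

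Both readings of 13.2 leave a difficulty. If the arms are pooled, opposite relations in the two arms can cancel, and a relation present in one arm can look like ordinary prognosis. If the coefficients are given by arm, the reader is left with two p-values side by side, and one significant and one non-significant result is easily taken as a difference.

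Two smaller points belong here. CRP enters the Pearson analysis with no stated transformation, although SAP 14.1.1 logs it for its own ANCOVA. In 12.3 the PaO2/FiO2 and WHO country results use the mITT set, while the overall clinical efficacy analyses use ITT (SAP 12).

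**Working it through.** The documents give no figure to reproduce: SAP 6 says the sample size was not derived from a statistical criterion.

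**Inputs from the documents.** About 30 patients per arm (SAP 6), 1:1 allocation (SAP 7), two-sided 0.05 (SAP 8), three countries (SAP 12.3).

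**Assumptions.** All correlations, slopes, effect sizes and country sizes below are mine; the documents give none.

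**1. Pooled correlation against interaction.** With equal arms, equal variances and no overall treatment difference, the pooled correlation is the average of the two arm correlations. On the Fisher z scale its SE is 1/√(60 − 3) = 0.132. The difference between two arm correlations has SE √(2/27) = 0.272. Power is approximately Φ(|z|/SE − 1.96).

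- r = 0.4 in both arms (purely prognostic). Pooled: 0.424/0.132 = 3.20, power 89%. The interaction is null, so it rejects in 5%.
- r = 0.4 on drug, 0 on placebo. Pooled r = 0.2: 0.203/0.132 = 1.53, power 33%. Interaction: 0.424/0.272 = 1.56, power 34%.
- r = +0.4 on drug, −0.4 on placebo. Pooled r = 0, nominal 5%. Interaction: 0.847/0.272 = 3.11, power 88%.

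Simulation agrees: pooled about 90%, 34% and 6 to 7%; interaction about 5%, 33% and 88 to 89%.

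A second simulation (4,000 trials, residual SD 1) shows the confusion directly. Slopes of 0.4 in both arms give a mean pooled r of 0.37, significant in 85% of trials. Slopes of 0 on placebo and 0.8 on drug give a mean pooled r of 0.35, significant in 78%. The pooled results are nearly the same for two different situations. The interaction test rejects in 5% and 82.5%.

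**2. Coefficients by arm.** Take the same true r = 0.3 in both arms. The SE at n = 30 is 1/√27 = 0.192, so 0.310/0.192 = 1.61 and the power in each arm is 0.363. The chance that exactly one arm is significant is 2 × 0.363 × 0.637 = 46%, with no true difference between arms.

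**3. What an interaction can detect at this size.** For 80% power the two arm correlations must differ by (1.96 + 0.84) × 0.272 = 0.76 on the z scale, for example r = 0 against 0.64.

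**4. Country.** The ANCOVAs repeated by country (SAP 13.1.1 and 14.1.1) contain treatment, so each country has its own drug-placebo contrast. With 20 patients per country, countries 0, 1 and 2 SD apart in prognosis and a true effect of 0.5 SD in each, the within-country estimates averaged 0.49, 0.50 and 0.50. Prognostic differences between countries therefore drop out.

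What is missing is the comparison:

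- The overall treatment effect has SE √(2/30) = 0.26 SD.
- With 20 patients per country, each country's effect has SE √(2/10) = 0.447, and the difference between two countries has SE √(0.447² + 0.447²) = 0.63.
- For the two countries listed first under sizes of 30/20/10 and 40/10/10, the SE of the difference is 0.58 and 0.71. Across the three layouts, the difference detectable with 80% power is 1.6 to 2.0 SD, and power for a 1-SD difference is 29% to 41%. Two countries of 10 patients each do worse: SE √(0.632² + 0.632²) = 0.89.

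Reading three within-country p-values instead is unreliable. With 10 per arm per country and the same 0.6-SD effect everywhere, power in each is 24.6%, and the three disagree on significance in 1 − 0.246³ − 0.754³ = 56% of trials. The range is 1 − 0.05³ − 0.95³ = 14% with no effect, up to 1 − 2 × 0.5³ = 75% when power is 50% in each. This applies to CRP and PaO2/FiO2, which carry a model by country.

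**The case against.** The strongest reply is that the documents name the aim as correlation, and a correlation analysis answers that. This stands in part. The plan nowhere says that it seeks effect modification or that it will choose patients for the next trial. A reader might infer that purpose, but the remark about planning future studies (SAP 6) concerns estimates of treatment differences. The point therefore rests on the unexplained contrast with 11.9 and on what a coefficient without treatment can show.

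Second, 13.2 may mean coefficients by arm. SAP 8 says summary tables are shown by treatment group with a total column, except efficacy tables, and one reading is that efficacy tables are by arm only. The pooled figures above would then describe an analysis nobody intends. That is possible, and Fisher-transformed coefficients with CIs could be compared informally. But no comparison is planned, and step 2 shows how often the two p-values would disagree by chance.

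Third, the sign-reversal case flatters the remedy. That stands: for r = 0.4 against 0 the interaction detects no more than the pooled correlation does (about 33% against 34%). Its advantage there is that it answers the right question.

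A reader might also infer that the country analyses confuse prognosis with drug effect. They do not, as step 4 shows. Nor do within-country p-values arise for the WHO scale, whose change SAP 13.1.4 summarizes descriptively. The missing log for CRP affects only the Pearson analysis, since Spearman is unchanged by it. The mITT/ITT difference is mostly formal in observed-case models, because a patient with no follow-up value contributes to neither.

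**Conclusion.** The point holds as a gap in SAP 13.2, with a lesser one in 12.3. In 13.2 no treatment term is specified and the pooling is unstated. A pooled coefficient cannot separate a prognostic marker from an effect modifier, and by-arm coefficients are not formally compared. In 12.3 the treatment effects by country are properly estimated for CRP and PaO2/FiO2, but nothing compares them.

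The size depends on assumed effects. Adding the interaction matters most where the marker works in opposite directions in the two arms (about 6 to 7% detection becomes 88 to 89%) and little for detection where it works in one arm only (about a third either way). At about 60 patients any interaction by biomarker or country will be imprecise, and a null result will not exclude an important one. The primary safety endpoint and the overall treatment estimates are untouched. This is a cheap improvement to exploratory analyses.

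**What to change.** **SAP 13.2.**

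- State whether the correlations are pooled or by arm, and keep them as descriptive.
- Add a linear model for change in PaO2/FiO2 at Days 7 and 14 with treatment, baseline PaO2/FiO2, baseline biomarker and treatment-by-biomarker, one biomarker at a time. Log CRP as in 14.1.1.
- Add an analogous model for change in WHO score.
- Report the interaction estimate with its 95% CI, and label it exploratory.

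**SAP 12.3.**

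- For CRP and PaO2/FiO2, fit one model with treatment, baseline, country and treatment-by-country.
- Show the country estimates and the treatment-by-country estimate with CIs from that model, without relying on p-values within each country.
- Use the same analysis set as the matching overall result.

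**Cost.** Some SAP wording, a few model statements and extra table rows, to be settled before unblinding. No new data or visits are needed. The text should say plainly that the interaction estimates will be wide at this sample size.

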13.3 Exploratory Analysis

As an exploratory analysis, to assess the effect of randomization stratification factors, an ANCOVA model with fixed effects for treatment, Dexamethasone use, and Remdesivir use and the Baseline score and age as continuous covariates will be fitted to the change from Baseline in PaO₂/FiO₂ ratio and CRP values.

The parameter estimates and corresponding P-values for each covariate, the LSMeans (standard error) for each treatment group, the LSMean difference between treatment groups, along with 95% CI of the treatment difference and P-value for treatment comparison will be presented.

The same statistical methods as described for preliminary efficacy endpoints in [Section 13.1.1 PaO₂/FiO₂ ratio](#) and biomarker [in Section 14.1.1 CRP Levels](#) will be followed for the analysis.

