### 6.2. Method of Treatment Assignment

All patients will be centrally randomized using an interactive response technology (IRT). Before the trial is initiated, the login information and directions for using the system will be provided to each site.

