7 RANDOMIZATION

Patients will be randomized to one of the 2 treatment groups: SIR1-365 100 mg or placebo at a 1:1 ratio. Randomization will be stratified according to age group (2 levels: < 60 or \geq 60 years), Dexamethasone use (2 levels: Yes or No), and Remdesivir use (2 levels: Yes or No).

Randomization will be controlled by a web-based Randomization and Trial Supply Management (RTSM) system.

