12.2 Adjustments for Covariates

Baseline measurement of the respective dependent variable will be used as a covariate in analysis of covariance (ANCOVA) models for selected efficacy variables.

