13.1.3 Number of days without oxygen use

Number of days without oxygen use during the study (Baseline to Day 28) will be summarized as a continuous variable by treatment. An estimate of the difference in mean numbers of days between SIR1-365 dose and placebo will be provided along with a corresponding 95% CI based on an ANOVA model with treatment as fixed effect.

The continuous duration (in days) where a patient's oxygen requirement is 'Room Air' will be derived using the date and time information from the 'O₂ Saturation' and 'Changes in Patient O₂ Requirements' eCRFs to calculate the cumulative days (including fractional days) on 'room air' through the end of calendar Day 28 where Day 1 is the day of the first dose of SIR1-365/matching placebo (or date of randomization if not treated). In the event that days/time on only room air are available after the end of day 28 that time (beyond the interval of interest) will not be included in the oxygen-free days.

The above analysis will also be repeated Baseline to Day 14.

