13.1.5 Days of hospitalization

Days of hospitalization after treatment will be determined using the ‘Study Drug Administration’ and ‘Hospitalization Details’ eCRFs. The date and time (in format 23:59) of 1st dose of study drug and discharge will be collected.

Duration of hospitalization after treatment up through 14 days will be calculated as

- Duration of hospitalization after treatment (days) = (Date and time of discharge – Date and time of 1st dose of study drug)/60/24

Missing discharge times will be assumed to be ‘23:59’ in order to calculate the maximum duration of time hospitalized. In the event a patient is hospitalized more than 14 days, 14 days will be used for analysis.

For patients that died within the first 14 days while hospitalized, the duration of hospitalization will be imputed as 14 days in order not to underestimate the number of days of hospitalization. In the unlikely event a patient dies within 14 days but subsequent to discharge, the number of days hospitalized will be 14 minus the number of days from discharge to death.

For patients with multiple hospitalizations in the first 14 days, the sum of all intervals will be calculated for analysis.

Duration of hospitalization after treatment as a continuous variable will be summarized descriptively by treatment and analyzed using a 1-way ANOVA model with a single term for treatment.

A similar analysis will be done for the total duration of hospitalization:

- Total duration of hospitalization (days) = (Date and time of discharge – Date and time of admission)/60/24

Missing admission times will be assumed to be ‘00:00’ and missing discharge times will be assumed to be ‘23:59’ in order to calculate the maximum duration of time hospitalized.

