Appendix 5: List of Tables, Listings, and Figures

The following proposal for Sections 14 and 16.2 is completed according to ICH E3² guidelines. The heading numbers and description are in **bold**. Minor changes from this planned index do not need to be amended in the SAP.

Index of Section 14

Table Number	Table Title
14.1	Demographic Data
14.1.1.1	Patient Disposition
14.1.1.2	Analysis Sets
14.1.1.3	Patient Visits
14.1.2	Number of Patients Randomized by Site and Treatment Group
14.1.3	Screen Failures
14.1.4	Demographic and Baseline Characteristics
14.1.5.1	Prior Medications by ATC Class and Preferred Term
14.1.5.2	Concomitant Medications by ATC Class and Preferred Term
14.1.5.3	Concomitant Medications Taken for COVID-19 by ATC Class and Preferred Term
14.2	Efficacy Data
14.2.1.1.1	Change in PaO ₂ /FiO ₂ Ratio from Baseline
14.2.1.1.2	Change in PaO ₂ /FiO ₂ Ratio from Baseline at Day 7 and Day 14 (LOCF)
14.2.1.2.1	Change in PaO ₂ /FiO ₂ Ratio from Baseline by Country - Subgroup Analysis
14.2.1.2.2	Change in PaO ₂ /FiO ₂ Ratio from Baseline by Country at Day 7 and Day 14 (LOCF) - Subgroup Analysis
14.2.1.3.1	Change in PaO ₂ /FiO ₂ Ratio from Baseline - Exploratory Analysis
14.2.1.3.2	Change in PaO ₂ /FiO ₂ Ratio from Baseline at Day 7 (LOCF) and Day 14 - Exploratory Analysis
14.2.1.4	PaO ₂ /FiO ₂ Ratio at Day 7 Using MMRM Model
14.2.1.5.1	Change in Derived PaO ₂ /FiO ₂ Ratio from Baseline
14.2.1.5.2	Change in Derived PaO ₂ /FiO ₂ Ratio from Baseline by Country - Subgroup Analysis
14.2.2.1	Summary of Time to Improvement of Oxygenation
14.2.3.1	Analysis of Number of Days without Oxygen Use (Baseline to Day 14)
14.2.3.2	Analysis of Number of Days without Oxygen Use (Baseline to Day 28)
14.2.4.1.1	Change in WHO Ordinal Scale from Baseline
14.2.4.1.2	Change in WHO Ordinal Scale from Baseline at Day 7, Day 14 and Day 28 (LOCF)
14.2.4.2.1	Change in WHO Ordinal Scale from Baseline by Country - Subgroup Analysis

14.2.4.2.2	Change in WHO Ordinal Scale from Baseline by Country at Day 7, Day 14 and Day 28 (LOCF) - Subgroup Analysis
14.2.4.3	Proportion of Patients with Clinical Improvement Defined by at least 2 Points Reduction in WHO Ordinal Scale
14.2.4.4	Summary of Time to Clinical Improvement Defined by at least 2 Points Reduction in WHO Ordinal Scale
14.2.5.1	Summary of Days of Hospitalization
14.2.5.2	Summary of Days of Hospitalization for Patients who Completed Treatment – Subgroup Analysis
14.2.6	Proportion of Patients with Respiratory Failure During Study

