14.2.7	Summary of All-Cause Mortality Rate
14.2.8	Correlation of Baseline Inflammatory Biomarkers with Clinical Efficacy Endpoints
14.2.8.1.1	Association of Baseline Inflammatory Biomarkers with Change in PaO ₂ /FiO ₂ Ratio from Baseline
14.2.8.1.2	Association of Baseline Inflammatory Biomarkers with Change in PaO ₂ /FiO ₂ Ratio from Baseline (LOCF)
14.2.8.2.1	Association of Baseline Inflammatory Biomarkers with Change in WHO Ordinal Scale from Baseline
14.2.8.2.2	Association of Baseline Inflammatory Biomarkers with Change in WHO Ordinal Scale from Baseline (LOCF)
14.2.9	Biomarker Data
14.2.9.1.1.1	Change in Plasma CRP Level from Baseline
14.2.9.1.1.2	Change in Plasma CRP Level from Baseline at Day 7 and Day 14 (LOCF)
14.2.9.1.2.1	Change in Plasma CRP Level from Baseline by Country - Subgroup Analysis
14.2.9.1.2.2	Change in Plasma CRP Level from Baseline by Country at Day 7 and Day 14 (LOCF) - Subgroup Analysis
14.2.9.1.3.1	Plasma CRP Level – Exploratory Analysis
14.2.9.1.3.2	Plasma CRP Level at Day 7 (LOCF) and Day 14 – Exploratory Analysis
14.2.9.1.4	Plasma CRP Level Using MMRM Model
14.2.9.1.5.1	Change in Plasma CRP Level from Baseline – PP Set
14.2.9.1.5.2	Change in Plasma CRP Level from Baseline at Day 7 and Day 14 (LOCF) – PP Set
14.2.9.1.6	Summary of Time to Reach 50% Reduction from Baseline in Plasma CRP Level
14.2.9.2.1	Change in Ferritin and White Blood Cell Counts from Baseline
14.2.9.2.2	Summary of Ferritin and White Blood Cell Counts, Time to First Time Back to Normal
14.3	Safety Data
14.3.1	Displays of Adverse Events
14.3.1.1	Overview of Treatment-Emergent Adverse Events
14.3.1.2	Analysis of Adverse Events

14.3.1.3	Treatment-Emergent Adverse Events by System Organ Class and Preferred Term
14.3.1.4	Treatment-Emergent Adverse Events by System Organ Class and Preferred Term with Onset <=7 Days, Onset <=14 Days and Onset <=28 Days of First Dose
14.3.1.5	Drug-Related Treatment-Emergent Adverse Events by System Organ Class and Preferred Term with Onset <=7 Days, Onset <=14 Days and Onset <=28 Days of First Dose
14.3.1.6	Treatment-Emergent Adverse Events by System Organ Class, Preferred Term and Maximum Toxicity with Onset <=7 Days, Onset <=14 Days and Onset <=28 Days of First Dose
14.3.1.7	Treatment-Emergent Adverse Events by System Organ Class, Preferred Term and Relationship with Onset <=7 Days, Onset <=14 Days and Onset <=28 Days of First Dose

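### Randomization is stratified by three factors, but the ANOVAs for oxygen-free days and hospital days omit them and no factor-adjusted version is planned

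*SAP*

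**What the plan says.** **Randomization.** SAP 7: "Randomization will be stratified according to age group" (below 60, or 60 and over), dexamethasone use (yes/no) and remdesivir use (yes/no), 1:1. That makes 2 × 2 × 2 = 8 strata for about 60 patients. Protocol 6.2 describes central randomization and names no strata.

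**Covariates.** SAP 12.2: "Baseline measurement of the respective dependent variable will be used as a covariate". No other covariate is named there.

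**Days endpoints.** For oxygen-free days, SAP 13.1.3 estimates the difference in means "based on an ANOVA model with treatment as fixed effect". For hospital days after treatment, capped at 14, SAP 13.1.5 says the duration is "analyzed using a 1-way ANOVA model with a single term for treatment", and it plans a similar analysis of total duration from admission. The table list in SAP Appendix 5 has no factor-adjusted table for any of these.

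**PaO2/FiO2 and CRP.** The main ANCOVAs (SAP 13.1.1 and 14.1.1) contain treatment and baseline. SAP 13.3 adds a second model: "As an exploratory analysis, to assess the effect of randomization stratification factors, an ANCOVA model with fixed effects for treatment", dexamethasone use and remdesivir use, with baseline and age continuous. It reports the adjusted difference, 95% CI and p-value. Tables are planned, for example "Plasma CRP Level – Exploratory Analysis".

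**Protocol.** Section 10.3.1 fixes treatment plus baseline for PaO2/FiO2 and treatment alone for oxygen-free days. Section 10.3.3 fixes treatment plus baseline for the log-scale biomarker ANCOVA. For hospital days, 10.3.1 names no model. SAP 15 declares no changes.

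**The concern.** Stratifying the randomization balances the factors between arms. Any outcome variance they explain then contributes almost nothing to the error of the treatment difference. A treatment-only linear model still counts that variance in its residual, so it reports a standard error larger than the true sampling error. The interval is wider than it needs to be and the test rejects less often than 5% under the null.

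What is at stake is precision. SAP 6 justifies 30 patients per arm partly by the estimates of treatment difference the trial will give for planning later studies, and intervals at that size are already wide. The gap is clearest for the days endpoints. For PaO2/FiO2 and CRP the reader will at least see an adjusted result.

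**Working it through.** The plan gives no figure to reproduce: 30 per arm is set without an effect size, SD or power.

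**Inputs from the documents:** N = 60, 1:1 allocation, three two-level factors, two-sided alpha 0.05.

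**Inputs assumed:** the share of outcome variance explained by the factors (R²; after baseline in the ANCOVA, on the latent scale for days) at 0, 0.05, 0.10 and 0.20; permuted blocks of 4 or 8; factor splits of 50/50/50% or 50/85/70%.

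**Closed form under perfect balance.** Residual variance is 1 without the factors and 1 − R² with them. So the SE ratio (unadjusted/adjusted) is 1/√(1 − R²), and the true error of the unadjusted test is about 2·[1 − Φ(1.96/√(1 − R²))].

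| R² | SE ratio | True error |
|---|---|---|
| 0.05 | 1/√0.95 = 1.026 | 0.044 |
| 0.10 | 1/√0.90 = 1.054 | 0.039 |
| 0.20 | 1/√0.80 = 1.118 | 0.028 |

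**Simulation.** Incomplete blocks leave some imbalance, so trials were simulated with permuted blocks in 8 strata and no treatment effect, fitting least squares with and without three main effects (8,000 to 10,000 replicates per setting). Ranges cover the block sizes and splits.

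| Endpoint | Quantity | R² 0.05 | R² 0.10 | R² 0.20 |
|---|---|---|---|---|
| ANCOVA (PaO2/FiO2, CRP) | SE excess | 2% | 4-5% | 11-12% |
| | True error, unadjusted | 4.3-4.8% | 4.0-4.3% | 3.1-3.6% |
| Hospital days, capped at 14 | SE excess | 2% | 4-5% | 9-10% |
| | True error, unadjusted | 4.4-4.9% | 4.0-4.5% | 3.3-3.8% |
| | CI half-width, 2.14 days unadjusted; adjusted: | 2.10 | 2.05 | 1.95 |
| Oxygen-free days | SE excess | 1-2% | 3-4% | 7-9% |
| | True error, unadjusted | 4.2-5.0% | 4.3-4.8% | 3.5-3.6% |
| | CI half-width, 4.4 days unadjusted; adjusted: | 4.35 | 4.3 | 4.1 |

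Hospital days were assumed lognormal (median 8, log-SD 0.7), with 10% deaths set to 14 as in SAP 13.1.5. Oxygen-free days were 28 minus lognormal oxygen days (median 9, log-SD 0.8), with 10% deaths scored 0; SAP 13.1.3 does not state a rule for deaths. With the factors in the model, error stays at 4.5-5.5%. In the ANCOVA simulation at R² = 0 the two SEs differ by less than 1%.

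**Where the excess lies.** In the ANCOVA at R² = 0.10 (50/50/50% splits, blocks of 4), the true sampling SD is 0.249 unadjusted and 0.248 adjusted, but the unadjusted model reports 0.260. The estimate is about as good either way; the reported SE is too large.

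**Second run** (6,000 trials per setting, treatment-only ANOVA against ANOVA plus factors, splits 50/70/50%, blocks of 4). The adjusted half-width is 0.95 of the unadjusted at R² = 0.10 and 0.90 at 0.20. At a difference of 0.72 SD, where 30 per arm gives about 80% power, power is 0.80 against 0.82 and 0.81 against 0.86.

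**What each R² requires.** With independent factors of equal effect d, in residual SDs, R²/(1 − R²) = d²·Σp(1 − p). For 50/50/50% splits the sum is 0.75; for 50/85/70% it is 0.25 + 0.1275 + 0.21 = 0.5875. So R² of 0.05, 0.10 and 0.20 need each factor to shift the outcome by about 0.26, 0.38 and 0.58 SD, or 0.30, 0.43 and 0.65 SD.

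Total hospital duration, which is uncapped, was not simulated. The direction is the same, but no size is given for it.

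**The case against.** The case for leaving the plan alone is fair. The study is exploratory, SAP 13.1 calls the secondary endpoints unpowered, and the treatment-only models follow the protocol. Adjusted PaO2/FiO2 and CRP results are already planned, so for those two the question is only which model leads. At R² of 0.05 to 0.10 the hospital-days half-width shrinks by just 2.14 − 2.10 = 0.04 to 2.14 − 2.05 = 0.09 days. The 20% case needs three fairly strong factors, and if nearly everyone receives dexamethasone or remdesivir (an assumption), that factor can explain little. All of this stands and limits the size. It does not remove the gap for the days endpoints, where no adjusted estimate exists and adding one costs almost nothing.

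A reader might go further, in ways the documents do not support:

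- *That the strata are ignored altogether.* SAP 13.3 uses all three variables. Entering age as continuous is defensible.
- *That the unadjusted results are biased or invalid.* They are unbiased, and the error is on the conservative side.
- *That Protocol 6.2 contradicts SAP 7.* It is silent on strata and the SAP supplies them.
- *That the Cox and competing-risk models lose precision in the same way.* They also carry treatment only, but a factor-adjusted hazard ratio is conditional on the factors and so a different quantity. The linear-model result does not carry over.
- *That the SAP 13.3 model should simply become the main one.* For CRP, 13.3 refers to change from baseline and LS mean differences, while SAP 14.1.1 and Protocol 10.3.3 analyse log CRP with back-transformed results. SAP 13.3 also says it follows the methods of 14.1.1, so its scale is unclear. Promoting it as worded could change the scale of the estimate as well as the covariates.

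**Conclusion.** The point holds as an optional gain in precision. The days ANOVAs omit the randomization factors, and no adjusted version is planned. If the factors are prognostic, the reported intervals are somewhat too wide: modest at an assumed R² of 0.20, small at 0.05 to 0.10, and nil in practice at zero. These sizes rest wholly on assumed R², factor splits, block size and outcome distributions. For PaO2/FiO2 and CRP the matter is only the ranking of analyses that will be reported anyway. The primary TEAE analysis is untouched. Severity: a change the sponsor could make, not one it must make.

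**What to change.** Before unblinding:

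1. **Days endpoints.** Add age group, dexamethasone use and remdesivir use, as randomized, as main effects to the ANOVAs in SAP 13.1.3 and 13.1.5, covering both the capped and the total hospital duration. Keep the treatment-only models as sensitivity analyses. Use main effects rather than eight stratum cells, since strata average only 60/8 = 7.5 patients.
2. **PaO2/FiO2 and CRP (optional).** Add the same factors to the main ANCOVAs of 13.1.1 and 14.1.1, stating whether age enters as the randomized group or as continuous. Keep the response scale as it is, with log CRP and geometric LS mean ratios. Do not promote 13.3 as worded.
3. **SAP 15.** Declare the departure from Protocol 10.3.1 for oxygen-free days and, if step 2 is taken, from 10.3.1 for PaO2/FiO2 and 10.3.3 for CRP. For hospital days the protocol names no model, so only the SAP text changes.
4. **Cox and competing-risk models.** Leave them as they are.

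The cost is three degrees of freedom (58 to 55 residual in the days ANOVAs with 60 patients), a declared departure and a few added table rows. No new data are needed: SAP 10.4 already summarizes all three factors.
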